### **6.3.3.6. Action Taken Regarding the Investigational Product**

The Investigator will provide information regarding the action taken with respect to the study treatment in response to the AE. Categories for action taken regarding study treatment will include none, drug interrupted, drug withdrawn, and not applicable.

### **6.3.3.7. Expectedness of an Adverse Event**

The expectedness of all AEs will be determined according to the most recent versions of the Investigator's Brochure.

### **6.3.3.8. Suspected Unexpected Serious Adverse Reactions**

Suspected unexpected serious adverse reactions (SUSARs) will be reported within the required timelines in an unblinded fashion to regulatory authorities and Institutional Review Board (IRB)/Independent Ethics Committee (IEC) per the requirements of the concerned competent authorities. SUSARs will also be reported in a blinded fashion to study Investigators

### **6.3.4. Recording of Adverse Events**

All AEs from the time of informed consent/assent through the last follow-up visit will be recorded in each enrolled patient's CRF. For patients who are found to be ineligible for the study during the Screening period and are not enrolled (ie, Screening failures), only SAEs will be recorded.

Information should include: a concise description of the event; date of event onset and resolution; determination of seriousness, severity, corrective treatment (if any), outcome, and relationship to IP or study procedure or underlying disease; and any action taken will be recorded. Resolution occurs when the patient has returned to his baseline state of health or further improvement or worsening of the event is not expected.

Whenever possible, a diagnosis will be recorded as an AE, rather than symptoms or isolated laboratory abnormalities related to that diagnosis. Several symptoms or laboratory results that are related to the same diagnosis can thus be part of the same AE. A medical or surgical procedure is not an AE; rather the condition leading to the procedure should be recorded as the AE. Similarly, death is not an AE, but is rather the outcome of the AE(s) that resulted in death. If the AE(s) leading to death are not known, then death must be reported as an AE. All AEs will be followed until the resolution of AE, completion of the patient's study participation, or study termination, whichever occurs first. SAEs will be followed until resolution or until the condition stabilizes or returns to baseline status.

### **6.3.5. Reporting Serious Adverse Events**

It is the responsibility of the Investigator that reporting is done adequately. In order to meet Regulatory reporting timelines, the study site is obligated to report any SAE(s) to the Sponsor or designee immediately and no later than 24 hours after receiving information of an event that meets at least one of the criteria for seriousness.

### **6.3.6. Special Situations**

#### **6.3.6.1. Overdose**

Refer to Section 6.4 for the definition of treatment overdose. An overdose is not an AE. An overdose will be reported even if it does not result in an AE. An overdose will be recorded on the Clinical Trial Safety Reporting Form and sent to the Sponsor or designee within 24 hours.

#### **6.3.6.2. Adverse Events of Special Interest**

All AESIs need to be reported to the Sponsor via email to PPD [REDACTED] within 24 hours of awareness, irrespective of the seriousness of the AE. In this study, the following AEs are considered of special interest:

##### Hepatotoxicity

CC1 [REDACTED]

##### Hypersensitivity

CC1 [REDACTED]

##### Thrombocytopenia

CC1 [REDACTED]

##### Rhabdomyolysis

CC1 [REDACTED]

#### **6.3.6.3. Death**

Death is an outcome of an event. All causes of death are SAEs. In the event of death, every effort should be made to obtain a death certificate and if possible, an autopsy report. If the cause of death is unknown, death will be recorded as the event.

#### **6.3.6.4. Unblinding due to a Medical Emergency**

In the event of a medical emergency, such as when knowledge of the patient's treatment assignment is essential for treating a patient due to an SAE, the Investigator has the option to unblind treatment assignment through the IXRS. If time permits, the Investigator must contact the unblinded CRO Medical Director before the unblinding of the patient. If time does not permit, the Investigator may authorize breaking of the blind, and then notify the unblinded CRO Medical Director.

The reasons for unblinding and the study personnel who were unblinded must be noted in the source documentation. The Investigator must not disclose information about treatment assignment to anyone who does not need the information for patient care. Disposition of patients who become unblinded due to medical emergency will be determined following discussion with the Sponsor.

The study will be unblinded once the last patient completes the **cci** visit; refer to the study unblinding plan for further details.

#### **6.3.7. Responsibilities of the Investigator**

The responsibilities of the Investigator include but are not limited to the following:

- Monitor and record all AEs.
- Determine seriousness, severity, and relationship to IP and/or study procedure and/or underlying disease.
- Determination of the onset and end date of each event.
- Provide initial report on all SAEs within 24 hours of first knowledge to the Sponsor via email to **PPD** or designee.
- Provide follow-up information on SAEs in a timely and proactive manner.
- Respond to queries regarding AEs and SAEs in a timely manner.
- Ensure source documentation for all AEs are accurate and complete.
- Ensure that the study is conducted as defined in this protocol.

Investigators may also report improvement of pre-existing DMD conditions or unexpected therapeutic responses.

#### **6.3.8. Responsibilities of the Sponsor**

The responsibilities of the Sponsor (Sarepta and designees) include, but are not limited to the following:

- Training of Investigator and site staff on AE/SAE definitions, safety assessments, and site obligations related to safety monitoring and reporting of AE/SAEs.
- Accurate and timely reporting of SUSARs to all applicable regulatory bodies, clinical trial Investigators, and other parties as appropriate and required within the regulated timelines.

- Ensuring accurate recording of AEs and SAEs.
- Notification of expedited SUSARs to sites.
- Annual safety reporting to regulatory authorities and IRBs/IECs according to regional requirements.

#### **6.4. Treatment Overdose**

For this study, any dose of SRP-9001 **cci** for a specific patient will be considered an overdose.

There is no recommended specific treatment for an overdose.

In the event of an overdose, the Investigator should:

1. Contact the CRO's unblinded Medical Director immediately.
2. Closely monitor the participant for any AE/SAE and laboratory abnormalities until resolution.
3. Document the quantity of the excess dose as well as the duration of the overdose on the Overdose Form and send to the Sponsor immediately. The overdose should also be entered in the CRF.
4. Provide appropriate medical care to patient based on clinical judgement.

Decisions regarding dose interruptions or modifications will be made by the Investigator in consultation with the CRO's unblinded Medical Director based on the clinical evaluation of the participant.

#### **6.5. Pharmacokinetics**

Pharmacokinetic parameters are not being evaluated in this study.

[figure not shown]
#### **6.6. Pharmacodynamics**

Creatine kinase levels will be measured at time points according to the SoA (Section 1.3).

Muscle biopsies will be performed at Screening/Baseline and at Week 12 in Part 1 **cci**.

[figure not shown]
#### **6.7.**

**cci**

**6.7.1.** [REDACTED]

CCI

**6.7.2.** [REDACTED]

CCI

[figure not shown]
**6.8. Biomarkers**

The collection of muscle biopsy samples [REDACTED] to assess micro-dystrophin [REDACTED] will be obtained; however, they are considered efficacy endpoints and described in Section 6.1.

[figure not shown]
**6.9.** [REDACTED]

**6.9.1.** [REDACTED]

CCI

CCI

**6.9.2. CCI**

[figure not shown]
CCI

## 7. STATISTICAL CONSIDERATIONS

### 7.1. Statistical Hypotheses

The study has 2 primary endpoints: change in quantity of micro-dystrophin protein expression from Baseline to Week 12 (Part 1) as measured by Western blot and change in NSAA total score from Baseline to Week 48 (Part 1). Each primary endpoint will be tested for statistical significance based on a multiplicity-adjusted testing procedure that will control the overall Type I error rate at a 2-sided level of 0.05. **cci**

Additional details will be specified in the Statistical Analysis Plan (SAP). The statistical analyses of endpoints in Part 2 will also be described in the SAP.

For the primary endpoint of change in quantity of micro-dystrophin protein expression from Baseline to Week 12 as measured by Western blot, the null hypothesis is that treatment assignment has no effect on the endpoint, and the alternative hypothesis is that treatment assignment affects the endpoint. Even though the alternative hypothesis is 2-sided, only superiority of SRP-9001 over placebo will be of interest.

The statistical hypotheses for other micro-dystrophin expression endpoints can be stated in a similar manner as those for change in quantity of micro-dystrophin protein expression from Baseline to Week 12 as measured by Western blot.

For the primary efficacy endpoint of change in NSAA total score from Baseline to Week 48 (Part 1), the null hypothesis is that the population means for the 2 treatments are equal and the alternative hypothesis is that the population means for the 2 treatments are not equal. Even though the alternative hypothesis is 2-sided, only superiority of SRP-9001 over placebo will be of interest.

The statistical hypotheses for secondary endpoints on physical function can be stated in a similar manner as those for change in NSAA total score from Baseline to Week 48 (Part 1).

### 7.2. Sample Size Determination

A dramatic treatment difference is expected for the primary endpoint of change from Baseline to Week 12 in quantity of micro-dystrophin protein expression as measured by Western blot. Therefore, the sample size is based on the power for the primary efficacy endpoint of change in NSAA total score from Baseline to Week 48 (Part 1) with Type I error of 0.05 (2-sided), assuming the alpha allocated for the other primary endpoint will be recycled. **cci**

### 7.3. Analysis Populations

For purposes of statistical analyses, the following analysis populations are defined:

[figure not shown]
[figure not shown]
[figure not shown]
Population	Description
Intent-to-Treat (ITT)	All randomized patients who received study treatment during Part 1, with treatment group designated according to randomization. The ITT population will be the main analysis population for endpoints for Part 1.
Per-Protocol	All patients in the ITT population who do not have important protocol deviations that may substantially affect the study results. Eligibility for the Per-Protocol population will be determined prior to breaking the study blind.
Safety	All patients who received study treatment during Part 1 or Part 2, with treatment group designated according to the treatment that they actually received.

## 7.4. Statistical Analyses

An SAP will be developed and finalized before database lock and unblinding of the study data. It will describe the details of the statistical analyses. This section is a summary of the planned statistical analyses of the primary and secondary endpoints as well as the safety analyses.

#### 7.4.1. Efficacy Analyses

The study has 2 primary endpoints: change in quantity of micro-dystrophin protein expression from Baseline to Week 12 (Part 1) as measured by Western blot and change in NSAA total score from Baseline to Week 48 (Part 1). Each primary endpoint will be tested for statistical significance based on the multiplicity-adjusted testing procedure that will control the overall Type I error at a 2-sided level of 0.05.

Endpoint	Statistical Analysis Methods
Primary	
For the primary endpoint of change in quantity of micro-dystrophin protein expression from Baseline to Week 12 (Part 1) as measured by Western blot, summary statistics will be provided by treatment group for Baseline, Week 12, and change from Baseline to Week 12 for quantity of micro-dystrophin protein expression as measured by Western blot.
 
CCI
             
	
For the primary efficacy endpoint of change in NSAA total score from Baseline to Week 48 (Part 1), summary statistics will be provided by treatment group for Baseline, each post-Baseline visit, and change from Baseline to each post-Baseline visit.
 
A mixed model with repeat measures or another test deemed appropriate, to be specified in the SAP, will be performed to compare the treatment groups for change

Endpoint	Statistical Analysis Methods
	in NSAA total score from Baseline to Week 48 (Part 1). The superiority of SRP-9001 over placebo will be concluded if the test achieves statistical significance based on the multiplicity-adjusted testing procedure that will be specified in the SAP.
Secondary	The secondary endpoints will be analyzed using similar statistical methods as the primary endpoints, as appropriate, with details specified in the SAP.
CCI	CCI [REDACTED]

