### 5.3.3. Randomization

Patients will be randomized in a 1:1 ratio by the IXRS in Part 1 of the study to receive either SRP-9001 or placebo. Patients randomized to SRP-9001 in Part 1 of the study will receive placebo in Part 2. Patients randomized to placebo in Part 1 of the study will have the opportunity to receive SRP-9001 in Part 2.

Randomization will be stratified by age group at Baseline (4-5 vs 6-7 years). To ensure approximately equal numbers of patients are assigned to the 2 treatment groups (SRP-9001 vs placebo) in Part 1, each age group must have a multiple of 4 patients.

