### **7.5.1. Interim Analysis at Week 12 in Part 1**

An interim analysis for micro-dystrophin expression will be performed after the blinded assays for micro-dystrophin expression for Baseline and Week 12 (Part 1) have been completed. Unless an unexpected outcome occurs at the interim analysis, there is no plan to change the conduct of the study after the interim analysis. A procedure will be put in place prior to unblinding of any personnel to micro-dystrophin expression data to ensure that the study continues to be conducted as a double blinded study after this interim analysis.

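### Does the open wording of the primary NSAA test, with no model terms listed and no explicit lock date, put the primary result at risk?

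*Combined protocol and SAP*

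**What the plan says.** Section 7.4.1 describes the NSAA comparison in one sentence: "A mixed model with repeat measures or another test deemed appropriate, to be specified in the SAP, will be performed" to compare the arms on change from Baseline to Week 48. No covariates are named, and no redaction falls inside that sentence. Section 5.3.3 says "Randomization will be stratified by age group at Baseline (4-5 vs 6-7 years", with 1:1 allocation. Section 3.1.2.1 gives up to 22 patients per arm.

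On timing, Section 7.4 says "An SAP will be developed and finalized before database lock and unblinding of the study data", and describes itself as a summary of analyses to be detailed in the SAP. Section 7.5 places the interim analyses and their multiplicity procedure in the SAP. Section 7.5.1 says "An interim analysis for micro-dystrophin expression will be performed after the blinded assays" for Baseline and Week 12 are complete. It requires a procedure, set up before any personnel see those data, to keep the trial double blind. Section 7.5.2 does the same for the Part 1 analysis, which is the primary one. Section 7.3 says "Eligibility for the Per-Protocol population will be determined prior to breaking the study blind", and makes ITT the main population for Part 1 endpoints.

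Section 7.2 says "A dramatic treatment difference is expected for the primary endpoint" based on Western blot, and that "the sample size is based on the power for the primary efficacy endpoint of change in NSAA total score", with "Type I error of 0.05 (2-sided), assuming the alpha allocated for the other primary endpoint will be recycled". The planning effect, SD and power are blacked out.

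**The concern.** Three features look uncomfortable together.

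- **The test is not fixed.** The wording keeps open an alternative to the mixed model, and the main clinical claim rests on this one comparison in at most 44 boys.
- **No terms are listed.** Baseline NSAA normally predicts change, and age group is the stratification factor. Leaving out baseline wastes precision. Leaving out a prognostic stratum gives standard errors that are too wide.
- **The lock point is loosely dated.** Sections 3.1.2.1 and 5.3.4 use unblinding for the whole-study event at a later visit. On that usage, neither the Week 12 interim nor the Part 1 primary analysis clearly counts as the unblinding in Section 7.4 or the breaking of the blind in Section 7.3. Since a very large Western blot difference is expected, expression data could reveal the arm to anyone who sees them.

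At stake would be some power, a choice of test that could not be shown to be blind, and a Per-Protocol list settled after the primary results exist.

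**Working it through.** **Inputs.** From the documents: 22 per arm, 1:1, two-sided alpha 0.05 (Sections 3.1.2.1, 5.3.3, 7.2). Assumed: the correlation rho between baseline and Week 48 NSAA, equal variance at both times, and the effect of age. The plan's own power figure cannot be reproduced because its inputs are blacked out.

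**What 22 per arm can detect.** By the normal approximation, d = (z for alpha/2 + z for power) × √(2/n).

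- 80% power: (1.960 + 0.842) × √(2/22) = 0.845 SD; by the noncentral t distribution, 0.865 SD.
- 90% power: (1.960 + 1.282) × √(2/22) = 0.977 SD; by noncentral t, 1.001 SD.

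**What baseline adjustment is worth.** The variance of the raw change is 2σ²(1 − rho). The residual variance after adjusting for baseline is σ²(1 − rho²). The ratio is (1 + rho)/2. Starting from 80% power without adjustment (d = 0.865, noncentral t):

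| Assumed rho | Variance ratio | Power with baseline term | Unadjusted patients per arm for the same precision |
|---|---|---|---|
| 0.5 | 0.75 | 90% | 22/0.75 = 29.3 |
| 0.7 | 0.85 | 86% | 22/0.85 = 25.9 |
| 0.9 | 0.95 | 82% | 22/0.95 = 23.2 |

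The gain is real, but it separates two possible SAPs. It is not a loss that the protocol imposes. The comparator is also a plain test on change, not the repeated-measures model that the protocol names first.

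**Leaving out the stratum.** In simulated null trials of 44 patients with age-stratified allocation, a test on change that ignored age had true error of 4.2% (rho 0.6) or 3.5% (rho 0.8) when age moved Week 48 NSAA by 0.5 SD, and about 2.8% to 3.3% with an age effect of 0.8 SD (rho 0.7). With age in the model it was about 5%. The error is conservative, so it cannot create a false positive.

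**Choosing the test.** Taking the smallest p-value among an adjusted, an unadjusted and a rank test raised two-sided error from 5% to between 6.4% and 7.9%. Best of five tests gave 6.9% to 7.8%. Both require Week 48 NSAA by arm. Section 7.5.1 covers Week 12 expression only. If the analyst knows arm and baseline NSAA but no outcome, and picks adjusted or unadjusted accordingly, one-sided error is 2.6% to 3.3% against a nominal 2.5%.

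**Timing, read across sections.** Western blot is a primary endpoint, tested under the SAP's multiplicity procedure (Sections 7.1, 7.4.1). It is analysed at the Week 12 interim (7.5.1). The interim procedure belongs in the SAP (7.5), and alpha from Western blot is assumed to pass to NSAA (7.2). To run the Week 12 analysis as described, the testing procedure has to exist by then. The protocol implies this order without stating it.

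**The case for a change.** The strongest case for a change is that the reserved alternative is more than missing detail: it is an option on the primary test. Read literally, the text lets the SAP be completed after Week 12 expression data have been seen, and the Per-Protocol list after the primary analysis. Nothing visible says that those who finalise the NSAA model are kept from the Week 12 data, and Section 7.5.4 allows a further interim. The remedy would be wording only, since baseline NSAA and age group are already collected.

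Part of this stands. The lock date is imprecise, and one named model with its covariates would read better. The consequences do not follow, though. A summary that lists no covariates does not exclude them; it lists no visit or covariance terms either. The safeguards in Sections 7.5.1 and 7.5.2 must be in place before anyone is unblinded. The Per-Protocol point touches a supportive analysis and cannot alter the ITT result. A fully prescribed model, with unstructured covariance and baseline-by-visit terms, would go beyond what can be judged here, because the visit schedule is redacted.

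**Conclusion.** The wording is open and the lock date is inexact, but no stated rule produces a wrong primary result. The SAP text is not part of the file reviewed, so it cannot be shown to omit baseline NSAA or age group. Adjusting for both is what an analyst would normally do after age-stratified randomisation.

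The possible cost is bounded. If the SAP left out baseline NSAA, the loss against an adjusted analysis would be about 2 to 10 percentage points of power for rho between 0.9 and 0.5, assuming 80% power without adjustment. Leaving out age would make the test conservative. Error of 6.4% to 7.9% is an upper bound that needs outcome data the Week 12 interim does not show; with arm and baseline alone the excess is at most about 0.8 points one-sided (3.3% − 2.5%). All of these figures rest on assumed correlations and age effects. This is a gap in detail that the SAP is meant to fill, and no change to the plan follows.

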#### 7.4.2. Safety Analyses

Four sets of safety analyses will be performed: (1) Part 1, this will provide summaries of safety endpoints in a side-by-side comparison between the two treatment groups that should be similar at Baseline; CCI [REDACTED]

[REDACTED] (3) Part 1 CCI [REDACTED], this will provide summaries of safety endpoints in a side-by-side comparison between the two treatment groups through Part 1 CCI [REDACTED]; (4) Time since SRP-9001 treatment, this will provide summaries of safety endpoints across all patients who received SRP-9001 in either Part 1 CCI [REDACTED], starting from the time of SRP-9001 infusion and continue through the end of the study.

Endpoint	Statistical Analysis Methods
Safety: TEAEs, and SAEs	Adverse events will be coded by the Medical Dictionary for Regulatory Activities. TEAEs include all AEs that occurred or increased in severity since the study treatment. A treatment-related TEAE will be defined as a TEAE that the Investigator considered possibly/probably or definitely related to the study treatment. TEAEs will be summarized by treatment group by the number and percentage of patients who reported TEAEs, with grouping by system organ class and preferred term. SAEs will be summarized in the same way. TEAEs will also be summarized by treatment group, with grouping by system organ class, preferred term, and severity. Further, treatment-related TEAEs will be summarized in the same way as TEAEs.
Safety: Clinical laboratory assessments	Clinical laboratory variables will be presented in 3 ways. First, change from Baseline to each scheduled assessment will be summarized descriptively by treatment group. Baseline will be defined as the value of the clinical laboratory variable obtained immediately before dosing of study drug (Day -1 for Part 1 and Day -1 for Part 2). For Part 1, if Day -1 value is unavailable, the value obtained at the Screening Visit will be used. Second, treatment-emergent potentially clinically significant (PCS) laboratory values will be identified. Criteria for PCS laboratory values will be defined in the SAP. Treatment-emergent PCS laboratory values will be defined as post-Baseline PCS laboratory values for patients whose baseline value for the same laboratory variable did not meet the PCS criteria. The number and percentage of patients with a treatment-emergent PCS laboratory value will be summarized by treatment group for each clinical laboratory variable. Third, the number and percentage of patients with abnormal, clinically significant laboratory values (per Investigator judgment) will be summarized by treatment group for each clinical laboratory variable.

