### 3.1.2.2. Part 2

Part 2 of the study will begin after the patient completes Part 1. Patients who were randomized to placebo during Part 1 will receive IV SRP-9001 ( $1.33 \times 10^{14}$  vg/kg) in Part 2. To maintain blinding throughout the study, patients previously randomized and treated with SRP-9001 in Part 1 will receive up to 10 mL/kg placebo (lactated Ringer's solution). Infusions will be given in the same manner as in Part 1.

CCI

- CCI
- CCI
- CCI

Prior to dosing in Part 2, if a patient has rAAVrh74 antibody titers > 1:400, consultation with the unblinded contract research organization (CRO) Medical Director, blinded Sponsor Medical Director, and PI is required prior to dosing. Patients who received placebo in Part 1 and who have rAAVrh74 antibody titers > 1:400 will not be dosed with SRP-9001 nor will they receive a second placebo infusion in Part 2. The patient will be encouraged to continue their follow-up through the last planned visit based on the protocol. If the patient decides to withdraw from the study, they should complete the last planned visit based on the protocol as their final visit.

The day prior to the study treatment (SRP-9001 or placebo) infusion in Part 2, the patient's dose of steroids will be increased to at least 1 mg/kg of a glucocorticoid (prednisone equivalent) daily and continue at this level for at least 60 days after the infusion unless earlier tapering is judged by the PI to be in the best interest of the patient.

CCI

On the day after the infusion, patients will receive a physical examination, have vital signs collected, and provide blood and urine samples before being discharged or in clinic, as applicable. CCI

CCI

Safety will be assessed by monitoring of TEAEs, SAEs, and select laboratory assessments.

Refer to Section 6 Study Assessments and Procedures for additional information.

### 3.1.2.3. Part 3

Part 3 of the study will be an open-label follow-up period. The study will be unblinded once the last patient completes the CCI visit; refer to the study unblinding plan for additional

details. Patients will have the opportunity to complete their 5-year post-infusion follow-up in a long-term extension study. The long-term extension study has been designed to provide a uniform approach to monitoring long-term safety and efficacy in patients who received an infusion of SRP-9001 in a clinical trial.

[figure not shown]

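### Does the second laboratory baseline at Part 2 Day -1 spoil the long-term SRP-9001 laboratory summaries?

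*Combined protocol and SAP*

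**What the plan says.** The laboratory row of the table in protocol Section 7.4.2 takes as baseline the value "obtained immediately before dosing of study drug (Day -1 for Part 1 and Day -1 for Part 2"). It adds one fallback: "For Part 1, if Day -1 value is unavailable, the value obtained at the Screening Visit will be used". The same baseline feeds two of the three laboratory presentations. One is change from baseline at each scheduled assessment. The other is treatment-emergent potentially clinically significant (PCS) values, meaning "post-Baseline PCS laboratory values for patients whose baseline value for the same laboratory variable did not meet the PCS criteria". On PCS the row also says: "Criteria for PCS laboratory values will be defined in the SAP". The third presentation, values the investigator judges abnormal and clinically significant, uses no baseline.

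The opening of Section 7.4.2 lists four safety sets. Set 1 is Part 1. Set 2 is redacted and set 3 partly so. Set 4 pools all SRP-9001 recipients, "starting from the time of SRP-9001 infusion and continue through the end of the study".

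Under Section 3.1.2.2, "patients previously randomized and treated with SRP-9001 in Part 1 will receive up to 10 mL/kg placebo". Part 2 follows a 48-week Part 1 (Section 3.1.2.1). Boys given placebo in Part 1 whose antibody titre exceeds 1:400 before Part 2 "will not be dosed with SRP-9001 nor will they receive a second placebo infusion in Part 2". The Safety population in Section 7.3 is grouped "with treatment group designated according to the treatment that they actually received".

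Section 7.4 says that it summarises the analyses and that the SAP will give the details. The file reviewed contains no SAP text.

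**The concern.** Nearly every boy has two infusions, and the baseline rule names a date before each of them without tying either to a safety set. For a boy given SRP-9001 in Part 1, Day -1 of Part 2 comes before a placebo infusion but about 48 weeks after the gene transfer. Set 4 follows him without a break across that date.

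If an analyst moved him to the second baseline from Part 2 onward, a lasting change after SRP-9001 would be subtracted away, and a change that resolved would look like a new change in the opposite direction. Boys first given SRP-9001 in Part 2 would keep a true pre-treatment baseline, so pooled rows at the same time since infusion would mix two quantities. The count of treatment-emergent PCS values rests on the same baseline. Set 4 is the visible analysis arranged by time since SRP-9001, so late laboratory changes are what it should show.

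Some neighbouring points look similar: no fallback for a missing Part 2 Day -1 value, no Part 2 dosing to anchor a baseline for boys excluded by titre, and no single treatment label for a boy with both infusions.

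**Working it through.** The plan states no figure for this point, so there is none to reproduce. The arm sizes do agree with the total: 22 + 22 = 44 (Sections 3.1 and 3.1.2.1).

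**Inputs.** Up to 22 boys treated early and up to 22 treated later; Part 1 of 48 weeks; Week 130 as the minimum follow-up before rollover (Section 3.1.2.3). Assumptions, not in the documents: k placebo boys not infused with SRP-9001 in Part 2 (0, 2 or 4), and d, the mean shift already present at Part 2 Day -1.

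**Reading A: a boy treated early is moved to the second baseline.** Let x0 be the value before SRP-9001, x0 + d the value at Part 2 Day -1, and y a later value.

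- Change from the first baseline: y − x0.
- Change from the second: y − x0 − d.
- Difference: −d, whatever y is.
- Pooled over set 4: −d × 22/(44 − k). This is −0.500d for k = 0, −0.524d for k = 2 and −0.550d for k = 4.
- Put another way, let a late shift be 1 unit, with a fraction r already present at Part 2 Day -1. The pooled mean is (22(1 − r) + 22)/44, which is 1.0, 0.875, 0.75, 0.625 and 0.5 for r = 0, 0.25, 0.5, 0.75 and 1.
- Follow-up of boys treated later, from SRP-9001 to Week 130: 130 − 48 = 82 weeks. If all of them stopped there, only boys treated early would contribute beyond 82 weeks and the error would be −1.0d.

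**Reading B: each boy keeps the last value before his SRP-9001 infusion.** The baseline is Part 1 Day -1 for boys treated early and Part 2 Day -1 for boys treated later. The error is 0 at every visit.

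**Which reading does the text support?** Set 4 has its time origin at the SRP-9001 infusion, and the laboratory baseline is the last value before dosing. Together these give Reading B. The rule has to name both dates because the two cohorts receive SRP-9001 in different parts. No sentence says that the second value replaces the first.

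**PCS counts, even under Reading A.** I enumerated PCS status (yes or no) at the first baseline, at Part 1 visits, at the second baseline and at later visits: 2⁴ = 16 patterns. Over the whole of set 4 the two readings disagree in 4, which fall into two situations:

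- The value is first PCS at Part 2 Day -1 itself (2 patterns; missed under Reading A).
- The value is PCS before SRP-9001, not PCS at Part 2 Day -1, then PCS again (2 patterns; newly counted under Reading A).

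A boy not PCS at the first baseline who becomes PCS at a Part 1 visit is counted under both readings. A persisting abnormality is lost only in a table restricted to Part 2, and no such table is visible.

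**The case for a change.** The strongest case for a change is that Reading B is sensible but unwritten. The term study drug does not settle the matter, since Section 5.3.4 has the blinded Treating Team manage the study drug infusion, so the term covers placebo too. The laboratory row shows no redaction, fixes the baseline itself and names only the PCS criteria as a matter for the SAP. A SAP that copied the row word for word would carry the ambiguity forward. The clarification would cost one sentence, and settling it before unblinding would prevent a choice made with the results in view.

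What stands is that the mapping of baseline to set is not written down. The rest is weaker.

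- The general deferral in Section 7.4 covers the whole section, and a baseline for each set is ordinary SAP content.
- The −d result is an identity that holds only if Reading A is adopted. The documents give no value for d, and d would also include 48 weeks of growth and disease progression.
- The −1.0d figure needs Part 2 dosing exactly at Week 48 and no later-treated boy followed past Week 130, although that visit is a minimum.
- Important late changes have routes that do not use this baseline: the third laboratory presentation, adverse event recording of clinically significant abnormalities (Section 6.2.4), GGT and GLDH checked against the upper limit of normal throughout (Section 6.2.5.1), and hepatotoxicity and thrombocytopenia as events of special interest (Section 6.3.6.2).
- The neighbouring points mostly fall outside the visible sets. A placebo boy excluded by titre never receives SRP-9001 and is not in set 4. Set 1 has one infusion per boy, and set 4 contains only SRP-9001 recipients, so neither needs a two-infusion label.

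**Conclusion.** No change to the plan follows. The silence is real: two baseline dates, four safety sets, and no statement linking them. But the set at issue starts at the SRP-9001 infusion, the baseline precedes dosing, and the two dates fit the two cohorts. An analyst deriving set 4 would take the last value before each boy's SRP-9001 infusion, and the error is then zero.

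The possible error of −0.50d to −0.55d in pooled means depends on a reading the text does not impose, on an undocumented d, and on an assumed 0 to 4 placebo boys left uninfused. The PCS count for set 4 would differ only in the two narrow situations shown. The summaries are descriptive, so sample size, power and Type I error are unaffected.

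This conclusion assumes that the SAP, which was not in the reviewed file, does not adopt the second baseline for boys treated early. Sets 2 and 3 are wholly or partly redacted and are not judged.
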